6.2. Patients unable to provide informed consent (England and Wales)

Some patients who are eligible for the trial will have a temporary impairment to their ability to provide consent. This impairment will result from the condition for which they require surgical intervention. Patients who have a long-term cognitive impairment that prevents fully informed consent will be excluded from the trial.

If the patient does not have capacity for fully informed consent due to temporary impairment, where possible the trial will be briefly discussed with them, and they will be given the Summary Patient Information Sheet. In accordance with guidelines from the Health Research Authority (HRA), the trial will also be discussed with the patient's relative or carer (Personal Consultee). The Personal Consultee will be asked if the patient has expressed any prior wishes with regard to participating in research and if the patient has expressed a preference then this will be adhered to. The relative is not asked to provide consent on behalf of the patient, but rather provide an opinion on the views and feelings of the potential participant.

The patient's relative/carer must be:

- Told that they are being asked to advise on the views and feelings they believe the adult would have towards participation in the study
- Told that they are free to decide whether they wish to provide this advice or not
- Given sufficient information, in an understandable form, about the study to ensure that they provide informed advice

A Consultee Information Sheet will be provided to facilitate the assent process. If the consultee agrees that the patient should be included in the trial, the consultee will initial, sign and date the latest version of the Consultee Declaration Form.

If no Personal Consultee is available, the patient will not be included in the trial.

It is imperative that when a Personal Consultee has been consulted, as soon as the participant is able to provide informed consent, the trial is explained to them and their written informed consent is sought. The participant will be given the Patient Information Sheet for delayed consent and their consent will be documented through the initialling, signing and dating of the latest version of the Informed Consent Form for delayed consent.

If, at any stage, the participant refuses consent for involvement in the trial or asks to be withdrawn from the trial, their wishes must be adhered to.

For a small number of patients (<2%) it is anticipated that they will not regain consciousness/capacity within 30 days, as these patients will have already received the intervention and reached the primary outcome, their data will be retained for use in the final analysis. If these patients regain capacity after 30 days, where practical, the local research team will consent them for their involvement in the study.

6.3. Patients unable to provide informed consent (Scotland)

Some patients who are eligible for the trial will have a temporary impairment to their ability to provide consent. This impairment will result from the condition for which they require surgical intervention. Patients who have a long-term cognitive impairment that prevents fully informed consent will be excluded from the trial.

If the patient does not have capacity for fully informed consent due to temporary impairment, where possible the trial will be briefly discussed with them, and they will be given the Summary Patient Information Sheet. In accordance with guidelines from the HRA, the trial will also be discussed with the patient's legal representative. For the purposes of SUNRISE, a patient's legal representative will be their nearest relative (See Appendix 1 for a hierarchical list of nearest relatives). Patients with long-term incapacity are not included in this trial so patients that have appointed a Welfare Attorney or Guardian will not be eligible.

The legal representative must be:

- Told that they are being asked to give consent on behalf of the incapacitated adult
- Told that they are free to decide whether they wish to make this decision or not
- Told that they are being asked to consider what the adult would want, and to set aside their own personal views when making this decision
- Given sufficient information, in an understandable form, about the trial to ensure that they can make an informed decision

A Legal Representative (Nearest Relative) Information Sheet will be provided to facilitate the consent process. If the legal representative consents for the patient to be included in the trial, the legal representative will initial, sign and date the latest version of the Legal Representative (Nearest Relative) Consent Form. If no legal representative is available, the patient will not be included in the trial.

It is imperative that when a legal representative has been consulted, as soon as the participant is able to provide informed consent, the trial is explained to them and their written informed consent is sought. The participant will be given the Patient Information Sheet for delayed consent and their consent will be documented through the initialling, signing and dating of the latest version of the Informed Consent Form for delayed consent.

If, at any stage, the participant refuses consent for involvement in the trial or asks to be withdrawn from the trial, their wishes must be adhered to.

For a small number of patients (<2%) it is anticipated that they will not regain consciousness /capacity within 30 days, as these patients will have already received the intervention and reached the primary outcome, their data will be retained for use in the final analysis. If these patients regain capacity after 30 days, where practical, the local research team will consent them for their involvement in the study.

6.4. Patients unable to provide informed consent (Australia)

Patients that are unable to provide informed consent in Australia will not be eligible to be enrolled in the trial.

7. RECRUITMENT AND RANDOMISATION

7.1. Participant identification and recruitment

Patients who may be eligible for inclusion in the study will be identified by either the consultant or trainee surgeon once the decision to take them to theatre has been made. Patients will be approached by a GCP trained member of the research team. This member of the research team may be either a member of the clinical team or a research nurse. The consent process will be undertaken as detailed in Section 6.

7.2. Screening logs

Screening logs will be kept in accordance with the CONSORT guidance and GCP, and filled in the ISF.

To aid completion of the SUNRISE Participant Screening Log, on a weekly or monthly basis a member of the research team will check the theatre logbook (paper or computer based depending on local arrangements) to identify patients who have undergone an emergency laparotomy but were not randomised into the trial. The reasons for non-randomisation will be recorded on the screening log. This information may be found by reviewing the patient record or liaising with the clinical team.

7.3. Randomisation

Following consent, the participant must undergo an emergency (non-elective) laparotomy as described in the inclusion criteria to be randomised into the study. If a participant becomes ineligible, due to either pre-operative events that occur post-consent or intra-operative findings, they will not be randomised. This will be recorded in the SUNRISE Participant Screening Log as well as the patient notes.

To minimise any potential for bias due to changes in closure technique caused by knowledge of the treatment allocation, randomisation will take place in theatre following commencement of skin closure. This timing of randomisation will also allow minimisation according to the actual operation findings and procedure performed.

Randomisation will be provided by an automated telephone randomisation system (available on **UK: [name]** and **AUS: [name]**) and a secure online randomisation system (available at <https://w3.abdn.ac.uk/hsru/SUNRISE>), both managed by a third party. Unique log-in usernames and passwords will be provided to those who wish to use the online system and who have been delegated the role of randomising participants into the study as detailed on the SUNRISE Site Signature and Delegation Log. Recruiting sites will be issued a unique trial centre ID number/code to allow use of the telephone system. Both the online and telephone systems will be available 24 hours a day, 7 days a week apart from short periods of scheduled maintenance.

After participant eligibility has been confirmed and informed consent has been received, and following emergency (non-elective) laparotomy, the participant can be randomised into the trial. Paper Randomisation Forms will be provided to investigators and may be used to collate the necessary information prior to randomisation. All questions and data items on the Randomisation Form must be answered as instructed on the Case Report Form (CRF) before a trial number and treatment allocation can be given by the randomisation service. If required data items are missing, the randomisation will not be completed. Only when all the required data items are provided can randomisation be performed and a trial number and treatment allocation be provided.

Participants will be randomised in theatre by the operative team following commencement of closure of skin. Participants will be randomised at the level of the individual in a 1:1 ratio. A minimisation algorithm will be

used within the randomisation system to ensure balance in the treatment allocation over the following variables:

- Degree of contamination (clean, clean contaminated, contaminated, dirty)
- Whether or not a stoma is present (yes, no)
 - *If a stoma is present, whether it was pre-existing or formed during the operation will also be ascertained. However, this distinction will not be factored in to the minimisation process.*
- Recruiting site

So that the randomisation process is not completely deterministic, a 'random element' will be included in the minimisation algorithm. Following randomisation, a confirmatory email will be sent to the P I and nominated key members of the research team for the site.

The Investigator must keep and maintain the SUNRISE Patient Identification Log, which links participants with their allocated trial number, and is not for submission to the Trials Office. The Investigator will also keep and maintain the SUNRISE Screening Log which will be kept in the ISF, and should be available to be sent to the Trials Office upon request. The SUNRISE Patient Identification Log and SUNRISE Screening Log should be held in strict confidence.

7.4. Informing the participant's GP

If the participant (or their Personal Consultee or legal representative) has agreed, the participant's GP should be notified that they are in the SUNRISE Trial, using the SUNRISE GP Letter.

7.5. Blinding

It is not feasible to blind either the participants or the inpatient wound assessors at day 7 to treatment allocation because the presence of the negative pressure dressing is clearly identifiable. The Day 30 wound review will be undertaken by a trained wound assessor who will be blind to treatment allocation and who has not previously been involved in the care of the participant. The importance of blinding will be explained to participants and they will be asked to not inform the wound assessor of their treatment arm.

8. TRIAL INTERVENTION

8.1. Trial Intervention

The trial intervention is the application of a SUNPD. The Smith and Nephew SUNPD is a CE-marked device, Therapeutic Goods Administration (TGA) approved, and available for routine clinical use throughout the UK and Australia. It will be used within its licensed indication in the SUNRISE Trial. The SUNPD will be left *in situ* until discharge from hospital or until day 7 post-operatively (whichever is sooner). The dressing should not be routinely changed but if, for a clinical reason, the dressing needs to be changed, it should be replaced with another SUNPD (there are two dressings supplied in each dressing box which will allow one change at no extra cost). This change of dressing should be recorded on the Wound Assessment Day 7 or on Discharge (if sooner) CRF.

The control is the surgeon's preference of dressing (which may be conventional occlusive dressings, skin glue or no dressing, but cannot be another SUNPD). These will be left *in situ* according to local practice. When conventional occlusive dressings are used, it is expected that most participants will have this changed in hospital and discharged with a dressing in place.

8.1.1. Standardisation of dressing placement

As part of site set up, training will be provided for the PI and all research team members delivering the intervention involved in the trial in the optimum method of placement of dressings (see section 4.2). This will be provided prior to site opening to recruitment. It will then be the responsibility of the local PI to ensure that new members of the local research team are trained on placing the dressing. A summary of the method of placement will be displayed on the wall in theatre and also available in the box in theatres where the dressings are kept.

SUNPD application training can be disseminated to the other members of the research team by the PI or nominated delegates, such as the associate PI/lead trainee and/or lead research nurse. This will be captured on the SUNRISE Site Signature and Delegation Log and SUNRISE Training Log.

8.2. Intervention Supply and Storage

8.2.1. SUNPD Supply

Supply of the SUNPD will be maintained at the participating hospital. An initial supply of the SUNPD will be delivered to each site prior to site opening. It will then be the responsibility of the relevant SUNRISE Trial Office to arrange for appropriate resupply and delivery arrangements to be in place at each participating hospital. The process for this will be explained during the Site Initiation Visit.

8.2.2. Dressing Storage

Appropriate arrangements must be made to ensure availability of the dressings when needed, while also ensuring that dressings supplied for the trial are not used for non-trial indications. It is recommended that the intervention dressings are stored in a marked 'SUNPD for SUNRISE Trial use only' box in the emergency theatre complex. Instead of the whole stock of dressings being stored in theatres, it is advised that the research nurse/PI/Lead trainee at each site keeps the majority of the dressing stock in a secure office and regularly re-supplies the theatre box.

8.3. Dressing application

Dressings shall be applied according to manufacturer's instructions and as shown during the site training sessions. A guideline for placement of the dressings will be provided for site use. A laminated copy of this will be provided for display in theatres used for emergency laparotomies and also for storage in the 'SUNPD for SUNRISE Trial use only' box.

Once the dressings have been placed and the negative pressure commenced, any leaks should be patched with the provided reinforcement strips. The second dressing that comes in each PICO pack should be kept with the participant and if the original dressing becomes saturated during the seven days of negative pressure, the old dressing should be removed and a new dressing applied. The patching of the dressing and replacement of the dressing can be undertaken by a suitably qualified and experienced member of the participant's clinical team. The dressings should otherwise be left in place until the pre-discharge / Day 7 wound inspection by a member of the research team. On the day of the wound assessment, the dressing will be removed by a member of the nursing staff or the research team. If the dressing has to be removed for any other reason, this should be recorded in the participant's medical notes. The timing and reason for removal will be recorded in the Wound Assessment Day 7 or on Discharge (if sooner) CRF.

It is important to note that this is a pragmatic trial with minimal interference with the usual practice of the operating surgeon. One step that is controlled within the protocol is the closure of skin. The skin should be closed by either sutures (can be interrupted or continuous) or skin closure staples. **Glue cannot be used as a primary skin closure method in either group.** If the participant is randomised to the control arm (i.e. standard dressing), glue can be used as a wound dressing (if this is the surgeon's normal practice).

Alternative methods of dressing are a conventional simple (not silver, honey or iodine) occlusive dressing or no dressing at all. Another type of negative pressure dressing cannot be used in the control arm.

8.4. Treatment Modification

Treatment modification is not expected to be relevant to this trial.

If the dressing is removed during a theatre visit within 7 days of the index laparotomy, the same type of dressing will be reapplied to the wound at the end of the procedure, i.e. if allocated to the SUNPD dressing, a SUNPD will be reapplied at the end of the operation. The treatment period remains 7 days from the index laparotomy. If the participant has been allocated to the control arm a dressing of the surgeon's choice will be applied as long as this is not a SUNPD. If the procedure takes place longer than 7 days after the original operation, regardless of the randomised allocation, at the end of the operation a dressing of the surgeon's choice will be applied (as long as this is not a SUNPD).

If the participant returns to theatre within 30 days, a Return to Theatre form should be completed by the research team in conjunction with the surgeon undertaking the surgery.

9. OUTCOME MEASURES AND STUDY PROCEDURES

9.1. Primary Outcome

The primary outcome is SSI within 30 days of surgery, as defined by the internationally accredited CDC criteria. Wound assessment will be conducted at day 7 post-operation or on discharge (whichever is sooner). It will also be performed at day 30 post-operation, by a blinded and trained wound assessor. The intervening period will be covered by a structured patient diary.

The following CDC definition will be used to identify an SSI:

- The infection must occur within 30-days of the index operation

AND

- The patient must have at least one of the following:
 - Purulent drainage from the wound
 - Organisms are detected from a wound swab
 - Wound opened spontaneously or by a clinician AND, at the surgical wound, the patient has at least one of: pain or tenderness; localised swelling; redness; heat; systemic fever ($>38^{\circ}\text{C}$).
 - Diagnosis of SSI by a clinician or on imaging

9.1.1. Training in diagnosis of surgical site infections

All research team members who are undertaking wound assessments will be required to undertake the online module for the diagnosis of surgical site infections. This will ensure standardisation of diagnosis and can be accessed via the trial websites (UK: www.birmingham.ac.uk/SUNRISE, AUS: <https://hmri.org.au/sunrise-trial>) or directly using this following link: <https://bctu-redcap.bham.ac.uk/surveys/?s=DFPM7YMKRJ>. The assessors will hold medical or nursing qualifications; for example, doctors, nurses, advanced care practitioners or physician associates.

9.2. Secondary Outcomes

- Length of hospital stay after surgery as measured from the date of index surgery to the date of discharge

- Wound complications within 30 days post-surgery as graded by Clavien-Dindo scale (see Appendix 2)
- Hospital re-admission for wound related complications within 30 days. These will include SSIs, wound breakdown/dehiscence, seromas and wound related pain
- Health-related Quality of Life assessed using the validated Short Form-12 (SF-12) questionnaire at baseline, and day 7 and day 30, and the EuroQuol-5 Dimension-5 Level (EQ-5D-5L) at baseline, day 7, day 14, day 21 and day 30. Pain at the site of the primary laparotomy will also be assessed, using a Likert scale of 1-10 at day 7 and day 30
- Serious adverse events up to 30 days
- Cost-effectiveness assessed using a patient diary for patient reported healthcare resource usage. Healthcare usage will be taken directly from the patient diaries and the costs attributable to this will be identified
- Patient acceptability of use of their dressing via an acceptability score using a Likert scale of 1-10 at day 7, reflecting participant's assessment of the acceptability of having the dressing
- In the UK only, Health professional's acceptability of use of SUNPD (via a survey of users). This will focus on the ease of application of the dressing, the care needed to maintain/monitor the dressing while it is in place and an overall assessment of health professional's experience of the dressing

9.3. Trial Assessments

9.3.1. Screening, consent and randomisation

Screening will be undertaken by the clinical team. The clinical team will ensure that the patient meets the eligibility criteria. Once the patient has been identified they will be entered onto the screening log.

The identifying doctors/nurse/research team member should provide the PIS to the patient. If they are included on the Site Signature and Delegation Log, consent can also be taken at this stage. If they are not on the delegation log, consent should be taken by a member of the site research team.

Once written informed consent has been obtained, the Randomisation Form can be populated with demographic data by the member of the research team, a baseline EQ-5D-5L and SF-12 questionnaires will be given to the participant to complete. The participant is to be guided to complete the questions based on their health and wellbeing prior to the start of the episode that requires surgery.

9.3.2. Intervention

Once the pertinent operative details are known they should be added to the Randomisation Form. Following commencement of closure of the surgical skin wound, the operative details can be added to the Randomisation Form and randomisation process can take place. The participant will be randomised to receive either SUNPD or the surgeon's preference of dressing. The relevant dressing will then be applied in the operating theatre.

The In-Theatre form will be completed at the end of the operation. If allocated to the intervention arm, the LOT number of the dressing used will be documented on the CRF. Where possible, the operation note should not document the dressing that is used to aid blinding at the Day 30 wound review. The operation note should document that the wound was dressed "according to SUNRISE Trial allocation" or equivalent.

9.3.3. Day 7 (or on discharge if sooner) assessment

At day 7 (assessment window: Days 5 to 10) or on discharge (whichever is first), the wound will be inspected to determine if there is any evidence of wound infection and whatever dressing is in situ removed to facilitate this. If the patient has a SUNPD in place this must be removed on day 7 at the latest. This means that if the

wound review is being performed on day 5, the dressing is removed on day 5 and the wound assessment is performed. If the wound assessment is being performed on day 9, the SUNPD is removed on day 7 and replaced with a standard dressing until day 9 when the wound is reviewed.

The wound inspection will be undertaken by a member of the research team who has been trained in the diagnosis of wound infections by undertaking the online module (can be accessed via the trial websites (UK: <http://www.birmingham.ac.uk/SUNRISE>, AUS: <https://hmri.org.au/sunrise-trial>), or directly using this following link: <https://bctu-redcap.bham.ac.uk/surveys/?s=DFPM7YMKRJ>).

As part of this wound inspection, the Wound Assessment Day 7 or on Discharge (if sooner) CRF will be completed, which includes asking the participant to rate their wound pain using a 10-point Likert scale. The participant will also be asked to complete EQ-5D-5L and SF-12 Quality of Life questionnaires and they will be given their outpatient diary. If the assessment at day 7 is undertaken when the participant is still an inpatient, the questionnaires will be completed using either the forms in the diary or separate Quality of Life questionnaires (as used at baseline). If the participant is being discharged before day 7 (and hence the wound assessment is being performed before day 7), the participant will be instructed to complete the EQ-5D-5L and SF-12 at day 7 post-operatively. These forms will be found in their Patient Diary.

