9.3.6. Day 30 assessment

At day 30 (assessment window: Days 30-44; with day 0 being the day of randomisation), a blinded review will take place. If an in-person wound assessment is not possible as the patient is not able to return for an outpatient or research visit to the hospital, this wound assessment is to be conducted using real-time remote video consultation. Telephone follow up assessments of the patient and their wound status can be used as a last resort. The wound will be assessed for an infection according to the CDC SSI criteria. As part of the assessment the highest Clavien-Dindo grade of wound complication that occurred since surgery will be recorded²⁶.

As part of this wound inspection, the Wound Assessment Day 30 CRF will be completed, which includes asking the participant to rate their wound pain using a 10-point visual analogue scale. The participant will also be asked to complete the Quality of Life questionnaires, EQ-5D-5L and SF-12, if they have not already done so in the Patient Diary. If no wound infection is evident then the participant will have completed the study.

Prior to undergoing the Day 30 review, the participant will have completed the Bluebelle wound healing questionnaire in the Patient Diary. This assessment will be repeated with the wound assessor as part of the Day 30 review and will allow SUNRISE to compare results with the Bluebelle questionnaire. However, if the participant remains an inpatient at the time of the Day 30 assessment, the questionnaire does not need to be completed by the patient or repeated with the wound assessor.

In order to encourage and facilitate patients to attend their in-person wound review at day 30 (where appropriate), their travel expenses in the form of taxi fares, public transport costs or parking charges will be supported.

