9.4. Schedule of Assessments

Activity/CRF		Pre-theatre	In-theatre	Day 7 post-op (-2/+3 days)	Day 14 post-op (± 2 days)	Day 21 post-op (± 2 days)	Day 30 post-op (+ 14 days)	Day 30+
Patient identification and screening		On-call surgical team						
Patient consent	• Standard	Patient & Member of the research team						
	• Delayed (UK only)	Consultee/Representative & Member of the research team		Patient & Member of the research team when capacity regained				
Randomisation form		Started pre-theatre by the research team	Surgeon or member of the research team					
In-Theatre form			Ideally an operating surgeon, or member of the research team					
Wound Assessment Day 7 or on Discharge (if sooner)^{1,2}				Member of the research team				
EQ-5D-5L		Completed by the participant		Completed by the participant	Completed by the participant	Completed by the participant	Completed by the participant	
SF-12		Completed by the participant		Completed by the participant			Completed by the participant	
Patient diary				Completed daily by the participant following discharge from hospital until they undergo the Day 30 wound review				Patients to continue with a diary if they have an ongoing SSI
Bluebelle wound healing questionnaire							Completed by the participant independently, and then by the participant with a blinded member of the research team reviewing wound	
Wound Assessment Day 30¹							Completed by a blinded member of the research team as an in-person or remote (video) review	
SAE reporting			All serious adverse events by member of the research team using SAE form or wound assessment CRF if excluded from expedited reporting					Related serious adverse events only
Return to theatre form			Member of the research team for any return to theatre following patient returning to theatre					
PI Declaration form for CFR data								Completed by PI at the end of each participant's involvement

¹ Assessment of pain undertaken by a member of the research team by asking the participant and recording the response on the CRF

² Score of patient acceptability of dressing undertaken by a member of the research team by asking the participant and recording the response on the CRF

Table 1: Table of assessments. Member of the research team is a person named on the local delegation log and given the assigned duty.

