14.2.2. Secondary Outcome Measures

The secondary outcomes for the trial include continuous, categorical and time to event data items.

Time to Event outcomes (Length of hospital stay after surgery):

These outcomes will be compared between treatment groups using survival analysis methods. Kaplan-Meier survival curves will be constructed for visual presentation of time-to-event comparisons. Mixed effects Cox proportional hazard models will be fitted to obtain treatment effects which will be expressed as hazard ratios with 95% confidence intervals.

Categorical outcomes (Wound complications, Hospital readmission for wound related complication(s), Serious Adverse Events):

For binary secondary outcomes, the number and percentage of participants reporting each outcome will be reported by treatment group. An adjusted relative risk and 95% confidence interval will be estimated from a mixed effects log-binomial regression model.

Continuous outcomes (QoL measures - SF-12 and EQ-5D, Likert scale for pain):

SF-12, EQ-5D-5L and the Likert scale for pain at the site of the primary laparotomy are all continuous data outcomes and therefore will be summarised using means and standard deviations. The data at both day 7 and day 30 will be compared between groups using mixed effects linear regression models to obtain an adjusted mean difference and 95% confidence interval. Data for the EQ-5D-5L is collected at baseline and days 7, 14, 21 and 30, and so as a secondary analysis this outcome will also be analysed using a mixed effects repeated measures model.

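### The day 7 pain score is taken at discharge when that comes first, so participants who leave before the day 5–10 window have an earlier score analysed as day 7

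*Protocol*

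**What the plan says.** Section 9.2 sets the outcome at fixed days: "Pain at the site of the primary laparotomy will also be assessed, using a Likert scale of 1-10 at day 7 and day 30". It makes no allowance for discharge. Section 14.2.2 lists the pain scale with the quality-of-life measures and says: "The data at both day 7 and day 30 will be compared between groups".

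The first score is collected at the first wound assessment. Section 9.3.3 times that visit: "At day 7 (assessment window: Days 5 to 10) or on discharge (whichever is first), the wound will be inspected". As part of the inspection, the "Wound Assessment Day 7 or on Discharge (if sooner) CRF will be completed, which includes asking the participant to rate their wound pain". The pain footnote to the schedule in section 9.4 says the same: "Assessment of pain undertaken by a member of the research team by asking the participant and recording the response on the CRF".

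For participants who leave before day 7, section 9.3.3 makes a separate arrangement for quality of life: "the participant will be instructed to complete the EQ-5D-5L and SF-12 at day 7 post-operatively", on forms in the Patient Diary. It makes none for pain, and the diary contents listed in section 9.3.5 include no pain item.

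Section 9.3.3 also has any dressing in place removed for the inspection. It does not say whether pain is rated before or after that. At day 30, section 9.3.6 asks the participant to "rate their wound pain using a 10-point visual analogue scale", whereas sections 9.2, 9.3.3 and 14.2.2 call the instrument a Likert scale.

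**The concern.** The outcome as defined and analysed is pain on a given post-operative day. The outcome as collected is pain at the first wound assessment, whose day is set by discharge for anyone leaving early. The protocol sees this problem for quality of life and solves it with the diary, but leaves pain, which sits in the same bullet of section 9.2, without a solution.

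The day of rating is thus fixed after randomisation and tied to length of stay. Section 3.1 lists shorter stay as a hypothesised effect of the SUNPD. If the dressing did change how many people leave early, or how early, the arms would be rated at different average times after surgery, and a difference in timing could pass for a difference in pain. An analysis plan cannot restore a day 7 value that was never collected, and adjusting for the day of rating would condition on something the treatment may itself affect.

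A second, weaker gap is the unstated order of rating and dressing removal. What is removed can differ by arm: a SUNPD in one; an occlusive dressing, glue or nothing in the other.

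**Working it through.** No figure in the protocol depends on this point, so the check is mainly a comparison of sections.

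**Window.** The schedule gives day 7 as -2/+3 days, so 7 - 2 = 5 and 7 + 3 = 10. This agrees with days 5 to 10 in section 9.3.3. The discharge alternative has no lower limit.

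**Three cases.**
- Still in hospital at day 7: pain and quality of life are both obtained around day 7, within the window.
- Discharged on day 5 or 6: pain is rated on day 5 or 6, inside the window; quality of life on day 7.
- Discharged on day 3, as an example: pain is rated on day 3, which is 7 - 3 = 4 days before the nominal day and 5 - 3 = 2 days before the window opens; quality of life is still completed on day 7. No later pain score is collected until day 30.

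Only the third case breaks the protocol's own window.

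**When timing produces bias.** If pain changes roughly linearly by *b* points per day, and the arms differ by *D* days in mean day of rating, then

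spurious difference = *b* × *D*.

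If discharge timing does not differ by arm, *D* = 0 and the mean bias is about zero. What remains is extra spread from mixing days, and a wrong label.

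**Scale, for illustration only.** The protocol gives no discharge distribution, pain trajectory or standard deviation. Assume *b* = 0.1 to 0.5, *D* = 0.25 to 1 day, SD 2 to 3, and the 336 per group of section 14.1:
- low end: 0.1 × 0.25 = 0.025 points; high end: 0.5 × 1 = 0.5 points;
- standard error = SD × √(2/336) = 0.154 (SD 2) to 0.231 (SD 3);
- ratio: 0.025/0.231 ≈ 0.1 to 0.5/0.154 ≈ 3.2 standard errors.

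With *D* = 0 added, the range runs from nothing to enough to alter a conclusion. It shows that the effect cannot be bounded from the document; it does not estimate it.

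**Dressing removal.** Section 9.3.3 removes whatever dressing is in place so that the wound can be inspected, and takes the pain score as part of the same inspection, with no order given. When the assessment falls after day 7, the SUNPD has already come off on day 7 and a standard dressing is worn until the visit. For early discharges, sections 8.1 and 8.3 leave the SUNPD on until the assessment, so this exception does not cover the group with the timing problem.

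**The case against.** The case against is substantial on everything except the timing mismatch.

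- **Removal pain.** A reader might infer that the score is mixed with pain from taking the dressing off. The protocol does not support that as fact: the order is unstated, the item asks about wound pain, and section 10.2 collects pain or discomfort related to the dressing as a separate adverse event. For assessments on days 8 to 10 the SUNPD is no longer there to remove. What stands is that the order is open, so contamination is possible and could differ by arm.
- **Who is affected.** A reader might count everyone who leaves before day 7. Discharges on days 5 and 6 fall within the declared window, so only earlier ones are mistimed by the protocol's own standard.
- **Size and direction.** A reader might assume that 30–50% leave early, pain falls 0.3–0.5 points per day and the SUNPD brings discharge forward by 1 day, and so obtain 0.30 × 0.3 × 1 = 0.09 to 0.50 × 0.5 × 1 = 0.25 points against the dressing. None of those inputs is in the protocol, and the range leaves out zero. Section 1.1 links infection to prolonged stay, so a shorter stay through fewer infections would act mostly on longer admissions, where the rating is made around day 7 anyway. This objection stands: a benefit showing up as worse pain is conditional, not expected.
- **Scale name.** Likert against visual analogue is a wording slip. Arms are compared within each visit, so it cannot bias the contrast.
- **The remedy.** A diary score is self-completed at home, whereas inpatients are asked by staff, and the dressing may be on or off. This is a real cost, though the home-completion difference is already accepted for quality of life.

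**Conclusion.** The timing point holds. Sections 9.2 and 14.2.2 promise and analyse pain at day 7, while sections 9.3.3 and 9.4 collect it only at the earlier of the day 7 visit and discharge. Participants discharged before the day 5–10 window have an earlier score treated as day 7. This is more than missing detail, because following the plan as written ties the measurement day to length of stay, itself an outcome the intervention is hypothesised to change.

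The size of any bias cannot be estimated from the protocol. It is about zero if early discharge does not differ by arm, and otherwise depends on the pain trajectory and the shift in discharge. In either case the time point is mislabelled and variability is added. Entry of removal discomfort into the score is possible, not established. Pain is a secondary outcome; the primary analysis and the sample size are untouched.

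**What to change.** - For participants discharged before day 7, add the 1–10 pain item to the diary's Day 7 page, beside the EQ-5D-5L and SF-12 they already complete there, and use that score as the day 7 outcome.
- Record the actual day of rating for everyone, and keep any score taken at an earlier discharge as a separate variable.
- State in section 9.3.3 that the rating on the wound assessment form is taken before any dressing is removed.
- Use one scale name in sections 9.2, 9.3.3 and 9.3.6.

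The cost is one diary item and a few sentences. The downside is some missing diary scores among early discharges, and a difference in mode between self-completion at home and being asked by staff in hospital. Both are already accepted for quality of life. The change concerns measurement only.
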